### **2.3.3. Per Protocol Efficacy Population (PPE)**

The Per-protocol Efficacy (PPE) population will include all randomized and vaccinated participants excluding participants with major protocol deviations expecting to impact the efficacy outcomes. The list of major protocol deviations to be excluded from the efficacy analysis will be specified in the major protocol deviations criteria document which will be finalized before database lock and unblinding. Any participant with an RT-PCR-confirmed RSV-mediated ARI with onset within 14 days after vaccination will be excluded from the PPE population. Participants who discontinue within 14 days after vaccination will be excluded from the PPE population as well.

The PPE population is the primary efficacy population. Sensitivity efficacy analyses will also be performed on the FAS.

For exploratory efficacy analyses focusing on data from the second RSV season only, the participants of Revaccination Subcohort A will additionally be excluded. For analyses focusing on data from the third RSV season, participants of Revaccination Subcohorts A and B will be excluded. For exploratory analyses focusing on data over season two and three and over all three RSV seasons, second and third RSV season data will be excluded for the participants of Revaccination Subcohort A, and third RSV season data will be excluded for participants of Revaccination Subcohort B. Participants who develop major MPDs expecting to impact the efficacy outcomes and occurring up to the considered season will be **additionally** excluded from the PPE when focusing on data including the second or third RSV season. For exploratory analyses focusing on data over season two and three and over all three RSV seasons, only the data of the season in which the major MPDs expecting to impact the efficacy outcomes occur and the data of the seasons thereafter will be excluded. Note that in case an ARI started in RSV Season 1 or 2 and continues during Season 2 or 3 respectively, all ARI information will be considered part of the first or second year analysis, regardless if they were collected during the second or third year.

## 2.4. Definition of Subgroups

The following subgroups will be investigated for the primary endpoint and for key immunogenicity assays:

- Age categories (65-74 years, 75-84 years,  $\geq 85$  years), as collected
- Risk Level (increased risk/ non-increased risk), as collected (CDC definition)
- Risk Level (CDC definition + Chronic Kidney Disease [CKD] + Diabetes), per Medical History assessment (increased risk/ non-increased risk)
- Sex
- Region (northern and southern hemisphere), if applicable
- Race
- Baseline Frailty (0-0.1: not frail, 0.11-0.2: pre-frail, 0.21-0.45: frail,  $>0.45$  most frail)

Demographic characteristics, study disposition, protocol deviations, safety, immunogenicity, and efficacy might also be analyzed by risk level.

Additional exploratory subgroup analysis may be performed.

## 3. INTERIM ANALYSIS AND DATA MONITORING COMMITTEE REVIEW

### 3.1. DATA MONITORING COMMITTEE REVIEW

The study will be formally monitored by an IDMC. In general, the IDMC will monitor safety data at regular timepoints to ensure the continuing safety of the participants. They will specifically focus on SAEs, adverse events of special interest (AESIs for subcohorts 2A, B, C and D) on

solicited and unsolicited AEs of grade 3 or higher, on unsolicited AEs (UAEs) leading to permanent discontinuation and on related UAEs. The analysis of AEs will be performed according to the specifications in Section 4.2.1. The IDMC members will be informed in case of related deaths and AESIs of study participants. In addition, the IDMC will formally monitor the efficacy endpoints at the time points specified below in the planned analysis plan.

[figure not shown]
A summary of the planned analysis is provided below, and in [Figure 1](#) (in case the study is performed in the NH only), and in [Figure 2](#) (in case the study is performed in both hemispheres).

In brief:

- If participants are only enrolled from the NH, the primary analysis will be performed at the end of the first NH RSV season, except if the incidence is exceptionally low (less than 18 observed RT-PCR-confirmed RSV-mediated lower respiratory tract disease (LRTD) events per Case Definition #2). **In that case, the independent data monitoring committee (IDMC) will perform an interim analysis (IA).** If successful, proof of concept is demonstrated. If proof of concept is not demonstrated at the IA and there is evidence for efficacy (assessed via conditional power), 2,000 new participants (Cohort 2) will be added to the study who will be vaccinated in the next NH RSV season and followed up for one RSV season. In that case, the ongoing participants (Cohort 1) will be stopped at the end of RSV season or 6 months after the last vaccination whatever comes later.
- If enrollment is spread over the NH and SH, a single IA may be performed during the NH or SH RSV season. **The IA will be performed by the IDMC at the earliest of 2 predetermined time points (i.e., database cut-off dates of 15 May 2020 and 15 August 2020) when at least 14 RT-PCR-confirmed RSV-mediated LRTD events per Case Definition #2 are observed. If the IA is successful, proof of concept is demonstrated.** If proof of concept is not demonstrated at the IA or if less than 14 events are observed at the second time point, the primary analysis will be performed at the end of the SH RSV season in a similar way as in a NH study only.

[figure not shown]

**Figure 1: Flow Chart in Case the Study is Performed at the Northern Hemisphere Only**

a Number of RT-PCR confirmed RSV-mediated LRTD cases (based on Case Definition #2)  
b The study will stop at the end of the RSV season or 6 months after vaccination, whichever comes later.  
 CP =conditional power, IA =interim analysis, IDMC =Independent Data Monitoring Committee, LRTD =lower respiratory tract disease, NH =Northern Hemisphere, PA =primary analysis, POC =proof of concept

**Figure 2: Flow Chart in Case the Study is Performed at the Northern and Southern Hemisphere**

a Number of RT-PCR confirmed RSV-mediated LRTD cases (based on Case Definition #2).  
b The study will stop at the end of the RSV season or 6 months after vaccination, whichever comes later.  
 If the number of participants enrolled in the NH is <5,500 but ≥18 RT-PCR-confirmed RSV-mediated LRTD events (using Case Definition #2) are observed in the NH before opening sites in the SH, no sites will be opened in the SH and the study will be performed as a NH study only.  
 CP =conditional power, IA =interim analysis, IDMC =Independent Data Monitoring Committee, LRTD =lower respiratory tract disease, NH =Northern Hemisphere, PA =primary analysis, POC =proof of concept, SH =Southern Hemisphere

So the IDMC will evaluate in an unblinded fashion whether superiority is established for at least one of the primary endpoints (at the early IA or at the end of the RSV season in the event that less than 18 RT-PCR-confirmed RSV-mediated LRTD events are observed) or whether futility (conditional power <60%) is shown for all 3 primary endpoints (at the end of the first RSV season in the event that less than 18 RT-PCR-confirmed RSV-mediated LRTD events are observed).

More details regarding the IDMC roles, responsibilities and way of working are included in the IDMC Charter. This SAP will also be used to support the IDMC analyses. The following sections are applicable for the IDMC analyses: Section 4.2, 4.4.1 and 4.4.2.

### **3.2. Unplanned Snapshot Interim Analysis**

An unplanned snapshot interim analysis may be performed to allow for early decision making on capacity planning for the Ad26 SARS-CoV2, which is being developed for the prophylactic immunization against SARS-CoV-2 infection, and Ad26.RSV.preF vaccines. This is especially important for the production capacity in 2020 and 2021. The results of this unplanned snapshot interim analysis will only be shared with select members of upper management not involved in the conduct of the study.

Since this unplanned snapshot interim analysis will only be used for internal decision making, will not further affect the conduct of the study, and it is not expected that the number of events will drastically change for the primary analysis, no type I error adjustment will be applied. The success of the study will solely depend on the results of the primary analysis.

For further details see the Executive Committee Charter.

### **3.3. Analysis 28 Days Post Second Vaccination in Revaccination Subcohorts A, B, C and D**

This analysis will be done for each Revaccination Subcohort (A, B, C, and D) and will include safety and immunogenicity data from the considered Revaccination Subcohort. The analysis will be performed on unblinded data. Data collected up to the time of the 28-day post-second vaccination visit for the last participant in the considered Revaccination Subcohort will be included in the analysis.

Details on the outputs needed for these analyses are included in Section 5.

### **3.4. End of Season 2 Analysis**

This analysis will include all efficacy, safety, and immunogenicity data collected during the second season. Data collected up to the time of the end of the second RSV season visit will be included in the analysis. If the number of RSV-positive cases observed during the second season is low, the efficacy analysis might be restricted to a listing of major efficacy endpoints in RSV-positive participants during the second RSV season.

Details on the outputs needed for this analysis are included in Section 5.

### **3.5. Analysis of Revaccination Subcohorts A and B, when Revaccination Subcohorts 2A and 2B have reached the 28 Days Post Third Vaccination Timepoint**

This analysis will be done separately for each Revaccination Subcohort (A and B) and will include safety and immunogenicity data from the considered Revaccination Subcohort. The analysis will be performed on unblinded data. Data collected up to the time of the 28-day post third vaccination visit for the last participant in the considered Revaccination Subcohort will be included in the analysis.

Details on the outputs needed for this analysis are included in Section 5.

### **3.6. End of Efficacy Study Analysis**

This analysis will include all efficacy, safety, and immunogenicity data collected until the end of the third RSV season. Efficacy data collected up to the end of the third season visit for the last participant will be included in the analysis. The analysis will be performed on unblinded data.

Details on the outputs needed for this analysis are included in Section 5.

### **3.7. Final Analysis of Revaccination Subcohorts (A, B, C, and D)**

This analysis will be done for each Revaccination Subcohort (A, B, C, and D) and will include safety and immunogenicity data from the considered Revaccination Subcohort. The analysis will be performed on unblinded data. Data collected up to the last visit for the last participant in the considered Revaccination Subcohort will be included in the analysis.

Details on the outputs needed for this analysis are included in Section 5.

## **4. FIRST RSV SEASON ANALYSIS**

### **4.1. SUBJECT INFORMATION**

Subject information will be shown for the FA. Certain outputs will also show the Safety subset, PPI, PPE sets for all subjects as well as for the risk level (increased risk/ non-increased risk) subgroups.

#### **4.1.1. Demographics and Baseline Characteristics**

Demographic characteristics and screening/baseline characteristics will be summarized with descriptive statistics per vaccine regimen based on the FA, Safety subset, PPI, PPE sets as well based on the risk level of the subjects.

The following demographic and baseline characteristics will be summarized.

- Sex (Female/Male)
- Age (years)
- Age (categorical, 65-74 years, 75-84 years,  $\geq 85$  years), as collected

- Race
  - Ethnicity
  - Region (northern and southern hemisphere), if applicable
  - Height (cm)
  - Weight (kg)
  - BMI (kg/m^2)
  - BMI (categorical, < 18.5 kg/m^2, 18.5 to < 25 kg/m^2, 25 to < 30 kg/m^2, >= 30 kg/m^2)
  - Smoking status
  - Risk Level (increased risk/ non-increased risk), as collected (CDC definition) \*
    - For subjects at increased risk additional subcategories are COPD, CHF, asthma, other chronic heart disease, other chronic lung disease (these categories will be defined based on the medical history of the participants)
  - Baseline Frailty
  - Baseline Frailty (categorical, 0-0.1: not frail, 0.11-0.2: pre-frail, 0.21-0.45: frail, >0.45 most frail)
  - Risk Level (CDC definition + CKD + Diabetes) (increased risk/ non-increased risk), determined by medical history review prior to database lock \*
  - Number of Comorbidities of interest, based on the categories (CESCAT) from the medical conditions of interest list (see Section 4.1.5.1)
- \*: If for a participant no medical history records are available then this participant is considered as a non-increased participant, when looking at risk level as collected and for the broad definition.

#### 4.1.2. Disposition Information

The number and percentage of subjects screened, subjects in the FA, PPI, PPE, Safety subset, subjects vaccinated and not randomized, subjects randomized and not vaccinated will be tabulated per vaccine group. The number and percentage of discontinued subjects (study discontinuation and vaccination discontinuation) with the reason of discontinuation will be tabulated for the FA, PPI, PPE and Safety subset per vaccine group, risk level subgroup and overall.

Also, the number of subjects and percentage per phase and period will be tabulated.

#### 4.1.3. Protocol Deviations

Major protocol deviations will be summarized, per vaccine group, increased level subgroup and overall.

There will be special attention to major PDs related to the COVID19 outbreak.

#### 4.1.4. Concomitant Medications

The analysis of concomitant therapies will be done using the WHO drug coded terms. Concomitant medications associated with SAE will be collected through the study, as well as concomitant medications associated with ARI episodes and with complications of ARI will be recorded for all participants during all ARI episodes for the duration of the RSV season.

There will be special attention to:

- analgesics/antipyretics such as acetaminophen, non-steroidal anti-inflammatory drugs (NSAIDs) and aspirin, that started being administered during 7 days following the vaccination (00:00 of day of vaccination + 7 days), based on the safety subset. The following codes will be used for this: N02A (OPIOIDS) and N02B (OTHER ANALGESICS AND ANTIPYRETICS), M01A (ANTIINFLAMMATORY AND ANTIRHEUMATIC PRODUCTS, NON-STEROIDS) and M01B (ANTIINFLAMMATORY/ANTIRHEUMATIC AGENTS IN COMBINATION). The classes will be added in a footnote in all related tables and listings
- all concomitant medications for the safety subset
- concomitant medications related to SAEs, based on the FAS
- new concomitant medications associated with RT-PCR confirmed RSV ARI episodes and with complications of RT-PCR confirmed RSV ARI based on the PPE set. New concomitant medications are defined as medications not available at baseline or medication with an increased dosage (see [Attachment 9](#): New Concomitant Medications for details), compared to baseline. Baseline medications are all medications reported prior to and at the day of vaccination. In case a baseline medication is reported multiple times then only the last available record reported prior to or at the day of vaccination will be used.

Based on their start and stop date, concomitant therapies will be reported in each applicable phase and period. For the use of analgesics/antipyretics which are taken on the day of vaccination, an exception is made in case the time is before vaccination. In this case, the concomitant medication is also allocated to the post-dose period.

If a concomitant therapy records misses components of its start and/or stop dates (day and/or month and/or year):

- In case of partial start or stop dates, the concomitant therapy records will be allocated to periods using the available partial information, without imputations. If, for example, only month and year are available, these will be compared to the month and the year of the periods, and the concomitant therapy record will be allocated to the period(s) where these date parts match. This rule may lead to assignment to multiple periods. The same rule applies for identifying whether a concomitant therapy was administered during 7 days following a vaccination. If for example, the vaccination was administered on the 30 December 2017 and the concomitant therapy start date is January 2018, then the concomitant therapy will be assumed to have started within 7 days of the vaccination.
- In case of a completely missing start date, the concomitant therapy will be considered as having started before the study.

- In case of a completely missing end date, the concomitant therapy will be considered as ongoing at the end of the study.

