#### **4.10. Therapeutic Interventions**

The following are considered as therapeutic interventions of interest:

- New/increased bronchodilator/nebulizer treatment
- New/increased corticosteroid prescription
- New/increased antibiotic prescription
- New/increased antiviral prescription

These will be taken from the concomitant medication pages of the eCRF based on [Attachment 5](#).

The ones linked to an ARI or complication of an ARI will be displayed.

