##### **4.10.1. Analysis Methods**

The PPE set will be used to analyze the use of therapeutic interventions.

Therapeutic interventions taken at baseline will be summarized for all subjects in the PPE set.

Moreover, the proportion of participants with any RT-PCR confirmed RSV disease utilizing new therapeutic interventions and those with RT-PCR-confirmed RSV-mediated LRTD based on the 3 case definitions utilizing new therapeutic interventions will be tabulated per group and the corresponding VE (1-relative risk) with an exact Poisson 95% 2-sided CI will be determined and graphically depicted with a forest plot, similar to the primary analysis.

Baseline and new interventions are defined as in Section [4.1.4](#).

Depending on their occurrence, the above might be repeated for the different subcategories of therapeutic interventions or for subgroups (with or without calculation of VE).

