**Attachment 9: New Concomitant Medications – Increase in dosage Calculation**

In case a participant receives the same medication with the same form at baseline and during an ARI episode, then in order to identify whether there was an increase in dose between baseline and ARI episode the medication dose will be calculated by multiplying the dosage per administration with the number of administrations per day or per week, as applicable for both timepoints and compared.

This rule applies for the following medication frequencies:

- Once weekly (1 time per week)
- Twice weekly (2 times per week)
- Three Times weekly (3 times per week)
- Four Times weekly (4 times per week)
- Twice Daily (BID)
- Twice per Month (BIM)
- Every two weeks (Every 2 weeks)
- Every four weeks (Every 4 weeks)
- Weekly (Every week)
- Once
- Per Year
- Every three months (Q3M)
- Daily (QD)
- Four times daily (Q1D)
- Monthly (QM)
- Every Other Day (QOD)
- Three times daily (TID)

For frequencies equal to ‘other’ at baseline, any change to one of the above frequencies will be considered an increase, given that the form remains the same.

For frequencies equal to ‘as necessary’ (PNR) or ‘occasional’, any change to another frequency or dose will be considered as an increase.

A change from ‘as necessary’ (PNR) to ‘occasional’ or ‘other’ will not be considered as an increase.

Moreover, capsule and tablet are considered the same form so to define if there was an increase the dose and the frequency will be used as defined above. The same applies for inhalant and aerosol.

For example:

Standardized Medication Name	Dose per Administration	Dose Units	Dose Form	Dosing Frequency per Administration Interval	Route of Administration	Timepoint
corticosteroids	50.0000	ug	AEROSOL	1 TIME PER WEEK	NASAL	Baseline
corticosteroids	50.0000	ug	AEROSOL	QD	NASAL	During ARI

Baseline dose is  $50 \times 1 = 50$  ug per week

During the ARI  $50 \times 7 = 350$  ug per week

This is considered an increase in dose for this medication.

Standardized Medication Name	Dose per Administration	Dose Units	Dose Form	Dosing Frequency per Interval	Route of Administration	Timepoint
GUAIFENESIN	600.0000	mg	TABLET	PRN	ORAL	Baseline
GUAIFENESIN	1200.0000	mg	TABLET	ONCE	ORAL	During ARI

This is considered an increase in dose for this medication since the frequency goes from as necessary to once.

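### Courses finished before vaccination count as baseline medication, so a repeat of the same drug and form at the same or lower dose for an RSV ARI is not counted as a new intervention

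*SAP*

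**What the plan says.** Section 4.1.4 of the SAP defines baseline: "Baseline medications are all medications reported prior to and at the day of vaccination". If a drug has several such records, "only the last available record reported prior to or at the day of vaccination will be used". It then defines the complement: "New concomitant medications are defined as medications not available at baseline or medication with an increased dosage" relative to baseline.

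Attachment 9 gives the test for a dose increase when drug and form are the same. The dose is obtained by "multiplying the dosage per administration with the number of administrations per day or per week" and compared between the two timepoints. Start dates, stop dates and course length play no part.

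Section 4.10 lists the interventions of interest in four classes, for example "New/increased antibiotic prescription", and restricts the display to those linked to an ARI or its complication. Section 4.10.1 imports the definitions: "Baseline and new interventions are defined as in Section" 4.1.4. Section 5.9.1 repeats the VE analysis for later seasons without setting another medication baseline.

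Separately, within its rules for incomplete dates, Section 4.1.4 says of a drug with no start date at all that "the concomitant therapy will be considered as having started before the study".

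**The concern.** Antibiotics, antivirals and oral steroids are often given as short courses. A fresh course for an RSV ARI after an older course has ended is a new prescription, which is what Section 4.10 sets out to count. Because the baseline definition has no ongoing condition and no look-back limit, the finished course becomes the comparator, and an unchanged or lower dose is read as continuing therapy.

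At stake are event counts in these exploratory analyses:
- the VE for new therapeutic interventions (4.10.1 and 5.9.1);
- the placebo odds ratios against the case definitions (4.10.2);
- the relationship table in 5.11, where a missed intervention can also move a participant into the category with none of the listed outcomes.

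The tables of baseline interventions in 4.10.1 are affected in the other direction: finished courses would appear as taken at baseline.

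**Working it through.** **1. Reproduce the plan's example.** Attachment 9 uses weekly dose = dose per administration × administrations per week. Baseline is 50 × 1 = 50 ug; during the ARI it is 50 × 7 = 350 ug. Since 350 > 50, this is an increase. The example reproduces.

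**2. Apply the written rule to a finished course.** A drug is new if it has no baseline record, or if its weekly dose exceeds that of the last baseline record. The doses below are assumed, only to exercise the rule; the SAP does not give them. The baseline course is 500 mg three times daily, or 500 × 21 = 10,500 mg per week.

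| Drug during the RSV ARI | Weekly dose | Baseline course | New under 4.1.4 | New if baseline must be ongoing |
|---|---|---|---|---|
| Same drug and form, same dose | 10,500 mg | finished | no | yes |
| Same drug and form, lower dose | 500 × 14 = 7,000 mg | finished | no | yes |
| Same drug and form, higher dose | 875 × 21 = 18,375 mg | finished | yes | yes |
| Different drug | 10,500 mg | no record | yes | yes |
| Same drug and form, same dose | 10,500 mg | ongoing | no | no |

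The two rules differ only in the first two rows. Attachment 9 also counts most changes from an as-needed, occasional or other baseline frequency as increases, so those repeats are kept too.

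**3. From a missed drug to a lost event.** Section 4.10.1 counts participants who use new interventions, pooled over the four classes. A participant is lost only if nothing else new or increased was linked to that ARI. Tables by class have less of this protection.

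**4. Later seasons.** Section 2.1 resets the efficacy baseline at Day 365 and Day 730, but Section 5.9 resets nothing for medications. On the written rule, a course that ended before Day 1 can still be the comparator in season 3.

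**5. Effect on VE.** Let a and b be the vaccine and placebo event counts, and let a fraction f be lost in each arm. The ratio (1−f)a / (1−f)b = a/b is unchanged. The approximate variance of the log rate ratio, 1/a + 1/b, is divided by (1−f), so the interval widens by 1/√(1−f). The SAP gives no f, so these values are assumptions:
- f = 0 (no finished courses recorded): 1.000
- f = 0.05: 1/√0.95 = 1.026
- f = 0.10: 1/√0.90 = 1.054

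**6. Effect on the placebo odds ratios.** Let p1 and p0 be the true proportions with a new intervention in the two groups compared, and let a share s < 1 be detected in each. The odds ratio becomes p1(1−s·p0) / [p0(1−s·p1)], which is closer to 1 than p1(1−p0) / [p0(1−p1)]. The pull is toward no association.

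**The case against.** The case against rests on five points.

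- **Narrow scope.** A reader might infer that any repeat antibiotic or steroid course is missed. The documents do not support that: higher doses, other drugs or forms, and most changes from irregular frequencies are counted. This limit stands and is built into the point.
- **Dependence on data collection.** The defect exists only if finished pre-vaccination courses are recorded, which is a protocol matter. If only current drugs are captured, nothing is lost. This stands as a limit on size. The look-back wording and the rule for multiple records suggest that earlier records are expected. Attachment 9 speaks of a participant receiving a drug at baseline, which could suggest current use, but Section 4.1.4 defines the term and does not say so.
- **Little inferential weight.** The analyses are exploratory, and drug history is fixed before randomised treatment. A reader might infer a biased VE or a loss concentrated in COPD and asthma. The SAP shows neither.
- **Missing start dates.** A reader might infer that an undated ARI drug automatically becomes baseline. The sentence sits among rules for allocating drugs to periods and to the seven-day window, and the SAP does not say that it feeds the baseline definition. Only an ambiguity remains.
- **Timing.** The definition of new medications entered with Amendment 1 (April 2020), and the current text is Amendment 7 (July 2022), after the season 1 primary analysis. A change now needs open labelling and a bridge to the season 1 results.

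**Conclusion.** The point holds in its limited form. Section 4.1.4 together with Attachment 9 misclassifies a fresh course as not new when the same drug and form was given in a course that ended before vaccination and the dose has not risen. That conflicts with the stated aim of Section 4.10.

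The size cannot be computed from the SAP. The 5 to 10% range is an assumption without a source. If it is read as the share of treated RSV ARIs that repeat an earlier drug, it is a ceiling on lost events, because of the pooling over classes. Even at that ceiling the approximate interval for the log rate ratio is only 2.6 to 5.4% wider. With few events, though, one or two lost cases can be visible, and Section 5 itself expects that RSV cases may be limited in seasons 2 and 3.

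The conclusion that VE stays roughly the same assumes similar loss in both arms, and so a vaccine effect that does not vary much with prior drug use. The primary endpoints are unaffected.

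**What to change.** Amend Section 4.1.4 so that baseline medications are those ongoing on the day of vaccination: started on or before that day, with a stop date that is missing or falls on or after it. Apply the Attachment 9 dose comparison to those records only. State a convention for partial stop dates.

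Add a sentence saying that the missing-start-date rule serves period allocation and does not by itself make an ARI-linked drug a baseline medication. The opposite rule, that every such drug started during the ARI, is not advised, because it could count undated long-term therapy as new.

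Because season 1 has been analysed, use the revised definition for all seasons in the end-of-efficacy analysis, show the season 1 results under the derivation already used alongside, and record the change in Section 1.6.

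The cost is a few sentences, one filter in the derivation, and a rerun of the season 1 intervention tables. The remaining downside is the judgement needed for partial stop dates. If the data hold no finished pre-vaccination courses, the filter changes nothing.
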